3.3.4 Overview of trial medication

Trial kits will be produced and labelled centrally. Trial kits will be labelled consecutively with a unique ID. The trial kits and drugs will be clearly labelled according to standard practices for clinical trials (see Appendix 1). Trial kits will be prepared and shipped to the participating sites on a regular basis. Once a trial kit is opened, the site investigator, the research nurse, and the principal investigator will be informed. The central pharmacy will keep a tally of all trial kits and make sure, along with the site investigator and the research

BIHCA Protocol – version 1.5 Page **30** of **84** nurse, that sites are always equipped with enough kits. The site investigator at each site will keep track of all delivered and used trial kits. Data on actual drug administration (see section 3.3.3) will be entered in realtime in an electronic case report form (see section 7). This will ensure optimal tracking of trial drug delivery and accountability.

3.4 Blinding

The trial will be double-blind; patients, investigators, and the clinical team will be blinded to the allocation. Only the pharmacy providing the blinded, numbered kits will be aware of the allocation. The pharmacy will not be involved with clinical care or outcome evaluation.

Placebo will consist of normal saline which is indistinguishable from sodium bicarbonate in that it is colorless and without any identifying features. The normal saline will be stored in containers that are identical to the sodium bicarbonate containers. Furthermore, except for the intended effect (i.e., an increase in pH) and a potential increase in sodium, sodium bicarbonate has no distinctive rapid effects resulting in possible identification. These effects will rarely be identifiable during a cardiac arrest. The risk of unblinding is therefore at an absolute minimum.

A sealed opaque envelope will contain the allocation assignment which will allow for emergency unblinding. These envelopes will be placed at a central location with staff available 24 hours per day. The clinical cardiac arrest team will be able to contact the staff via phone and are therefore able to unblind in real-time. The decision to unblind will be at the discretion of the treating physician and clinical team. However, we do not expect scenarios where emergency unblinding will be necessary. In case unblinding occurs, the reason will be clearly documented in the case report form, and the patient will remain in the trial.

3.5 Trial procedures

3.5.1 Patients

The trial procedures will be limited to the interventions given during the cardiac arrest (see section 3.3) and the telephone interviews for long-term follow-up (see section 5.3 and 5.5). There will be no planned blood draws, other interventions, or additional procedures. Data will be obtained from the trial-specific case report form, the electronic medical records, and the Danish IHCA registry (DANARREST) (see section 7).

3.5.2 Clinical personnel

Prior to the beginning of patient enrollment and continuously throughout the enrollment period, the clinical teams involved in IHCA resuscitation at the participating hospitals will be informed about the trial. Clinical personnel will be informed about the background and objectives of the trial, the inclusion/exclusion criteria, the interventions, and the trial procedures they are involved in (see section 3.3.3 and 9.3.2). A demonstration of correct procedures using the trial kits will be included. Online education material will be available throughout the trial.

4. SETTING AND PATIENT POPULATION

4.1 Setting

The trial will be conducted at 21 hospitals in Denmark. All participating sites have clinical experience and expertise in treating IHCA patients.

4.2 Inclusion criteria

Inclusion criteria:

- 1) IHCA
- 2) Age \geq 18 years
- 3) Received at least one dose of adrenaline during cardiopulmonary resuscitation (CPR)

Cardiac arrest is defined as unconsciousness, abnormal breathing, and a loss of pulses requiring chest compressions and/or defibrillation. IHCA is defined as any individual with a cardiac arrest on hospital grounds, in locations that are covered by the local IHCA team. This will include patients who re-arrest in the emergency department or elsewhere after an OHCA if they, prior to the re-arrest, had sustained ROSC (i.e., spontaneous circulation for at least 20 minutes).

These broad inclusion criteria were chosen to reflect the pragmatic scope of the trial and to allow for optimal external validity.

4.3 Exclusion criteria

Exclusion criteria:

- 1) Clearly documented "do-not-resuscitate" order prior to the cardiac arrest
- 2) Prior enrollment in the trial
- 3) Invasive mechanical circulatory support at the time of the cardiac arrest

BIHCA Protocol – version 1.5 Page **32** of **84**

- 4) Known or suspected pregnancy at the time of the cardiac arrest
- 5) Known objection by the patient to participate in the trial
- 6) Clinical indication for bicarbonate administration

Occasionally, CPR is inadvertently started in patients with a pre-existing "do-not-resuscitate" order. If a "donot-resuscitate" order is clearly documented in the electronical medical record prior to the cardiac arrest, the patient will be excluded.

Patients previously included in the trial will be excluded to avoid statistical complexity related to correlated data.

Mechanical circulatory support includes extracorporeal circulation and left ventricular assist devices. Patients having an IHCA while on mechanical circulatory support constitute a very specific patient population with different characteristics and outcomes. They will therefore be excluded.

Patients with known or suspected pregnancy will be excluded. Cardiac arrest during pregnancy is exceedingly rare⁷⁰ and we expect that this exclusion criterion will lead to only few, if any, exclusions. If pregnant patients are included (i.e., if the pregnancy is not known and not obvious), we do not expect any harm to the patient or fetus as a result of the trial's intervention or placebo. Guidelines recommend that cardiac arrest in pregnancy is treated according to usual guidelines including intra-cardiac arrest medications.⁷¹ We note that, out of 2,362 patients assessed in our previous IHCA trial, only one was pregnant.³⁴

Patients will not be included in the trial if the enrolling investigator is aware that the patient has objected to participating in the trial (see section 9.2.3).

Administration of bicarbonate is recommended in rare occasions when hyperkalemia and certain toxicological causes of cardiac arrest are suspected.^{18,55,56} If the treating clinician believes there is a clinical indication for administration of bicarbonate during the cardiac arrest, and prior to randomization, the patient should not be included. This assessment will be made by the clinicians at the time of the cardiac arrest consistent with current clinical care.

4.4 Co-enrollment

There will be no general restrictions on entry into other clinical trials although this will be evaluated on a case-by-case basis.⁷² We are not aware of any ongoing or planned trials in this patient population in Denmark.

5. OUTCOMES

5.1 Primary outcome

5.1.1 Definition

The primary outcome will be ROSC. ROSC will be defined as spontaneous circulation with no further need for chest compressions sustained for at least 20 minutes. This definition is consistent with our previous trials^{34,54}, the *Get With the Guidelines® – Resuscitation* registry⁷³, the Danish registry for IHCA (DANARREST)⁷⁴, and the Utstein guidelines⁷⁵. If a patient is placed on extracorporeal circulation during the cardiac arrest, the patient will only be considered to have ROSC if they are able to be successfully weaned from the extracorporeal circulation with spontaneous circulation for at least 20 minutes.⁷⁶

5.1.2 Rationale

The rationale for any intra-cardiac arrest intervention is primarily to increase the rate of ROSC to subsequently improve the rate of meaningful survival. Since ROSC is a prerequisite for more long-term survival and since the focus of this investigation is an intra-cardiac arrest intervention, ROSC is a logical and meaningful primary outcome. ROSC is a core outcome measure in both the IHCA⁷⁵ and OHCA⁷⁶ Utstein guidelines and is suggested as a potential primary outcome measure by the American Heart Association⁷⁷.

5.2.2 Rationale

Survival at 30 days and survival at 30 days with a favorable neurological outcome are considered key outcome measures in cardiac arrest research.^{77,79,80} All follow-up survival data will be obtained from electronic medical records, the Danish Civil Registration System, or telephone follow-up, which allows for accurate and virtually complete follow-up.⁸¹

A centrally located, trained, blinded researcher will assess mRS using a standardized telephone interview, which ensures good reliability.⁸²⁻⁸⁴ In case the patient is still hospitalized, the interview might be performed in-person. Assessment of neurological outcome by telephone is valid and reliable.⁸⁵ If the patient is not able to participate in the interview, the interview will be conducted with a close relative or secondarily clinical personnel if the patient is admitted. The same standardized interview will be used. The dichotomy with favorable scores of 0-3 and unfavorable scores of 4-6 is widely used in cardiac arrest research and is consistent with recent cardiac arrest trials.^{54,86}

In accordance with the recent Core Outcome Set for Cardiac Arrest (COSCA)-initiative, we will also assess the Cerebral Performance Category (CPC).⁸⁷ CPC will not be considered a key outcome of neurological status.

5.3 Tertiary outcomes

We will include 90-day survival as a measure of long-term survival. 90 days were chosen since it is unlikely that later mortality will be directly linked to the cardiac arrest or the trial intervention. 90 days is also consistent with recommendations from the American Heart Association.⁷⁷

Health-related quality of life at 30 and 90 days will be assessed by the EQ-5D-5L questionnaire,⁸⁸ which is supported by the American Heart Association⁷⁷ as well as the COSCA-initiative⁸⁷. EQ-5D-5L is a generic approach with five items covering symptomatic, physical, psychological, and social consequences of a disease. It is preferred to HUI3 and SF-36 because it is free to use and requires a shorter interview. Assessment of health-related quality of life by telephone is valid and reliable.⁸⁹ EQ-5D-5L allows for potential future cost-effectiveness analyses and comparison to the background population.

During the same 90-day interview, we will reassess neurological outcome (mRS and CPC).

In addition to the above, we will collect outcome data on early cardiovascular function, laboratory values, organ failure, and hospital disposition.

To assess cardiovascular function and organ failure, we will calculate the Sequential Organ Failure Assessment (SOFA)-score⁹⁰ at 2, 24, 48 and 72 hours after the cardiac arrest in those alive. The SOFA score is a validated and widely used measure of organ failure assessing the respiratory, nervous, cardiovascular, hepatic, coagulation, and renal systems.⁹⁰ We will assess both the cardiovascular sub score as well as the overall SOFA score. The calculation of the SOFA score will be based on available clinical and laboratory data. Laboratory and clinical data closest to the given time point will be used. If a given component (e.g., bilirubin) is not available it will be assumed to be within normal ranges. If PaO₂ values are not available, they will be imputed using imputations based on SpO₂ values.^{91,92}

Laboratory values, including pH, standard bicarbonate, PaCO₂, potassium, calcium, sodium, and lactate from the first arterial (or venous) gas will be compared between groups.

Hospital disposition (e.g., home, rehabilitation, nursing home, hospice) will be defined at the time of discharge from an acute care hospital.

All outcomes recommended by the recent COSCA initiative (Core Outcome Set for Cardiac Arrest) are included in the present study.⁸⁷

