6. SAMPLE SIZE CALCULATION AND STATISTICAL ANALYSIS PLAN

6.1 Sample size calculation

The trial will be powered to the primary outcome of ROSC. From the VAM-IHCA trial, which had similar inclusion and exclusion criteria, the proportion of patients with ROSC in the placebo group was 33%.³⁴ Based on an absolute difference of 10% between the placebo and the bicarbonate group, we anticipate that 33% in the placebo group and 43% in the intervention group will obtain ROSC. This corresponds to a relative increase of 30%. With such estimates, an alpha of 0.05, and the use of the Fisher's Exact test, we will need a total of 778 patients to have 80% power to detect a statistically significant difference between groups. Given that the primary analysis will be adjusted for strong prognostic factors (see section 6.2.2 and 6.2.4), we will obtain additional power.^{115,116} The trial therefore has a minimum of 80% power.

We anticipate no loss to follow-up for the primary outcome (see section 6.2.7). Patients who withdraw consent and request deletion of data will not be replaced. Of note, no patients withdrew consent in our previous trials.^{34,54}

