6.2.3 Continuous outcomes

Continuous data will be presented as means with standard deviations (SD) or medians with first and third quartiles depending on the distribution of the data. Differences between groups in continuous outcomes are presented as mean differences with 95% confidence intervals obtained from a generalized linear model with robust errors with adjustment for prognostic variables (see section 6.2.4). If the data are severely non-normally distributed, other methods (e.g., transformation of the outcome, quantile regression, Hodges–Lehmann median difference) will be considered or the data will be presented descriptively.

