6.2.4 Adjustment for prognostic factors

To increase power, we will adjust all outcome comparisons for strong prognostic factors.^{115,116} These will include age, whether the cardiac arrest was witnessed, and the initial rhythm. Age will be included as a linear continuous variable¹²² and the initial rhythm (shockable [ventricular fibrillation or ventricular tachycardia] or non-shockable [asystole or pulseless electrical activity]) and witnessed status as binary variables. A recent meta-analysis found that these variables are strongly associated with survival after IHCA.²⁵ To confirm that these variables are also strongly correlated to ROSC and other relevant outcomes in the Danish setting, we performed multivariable logistic regression with age, witnessed status, and initial rhythm as the independent

variables and various outcomes as the dependent variable using data from the VAM-IHCA trial (n = 501).³⁴ As can be seen in Table 3, these variables were strongly associated with outcomes.

Variable	Odds ratio (95%CI)					
	ROSC	30-day survival	30-day favorable			
		So-day Survivar	outcome (mRS 0-3)			
Age (per 10-year increase)	0.88 (0.70, 0.95)	0.67 (0.54, 0.82)	0.63 (0.49, 0.81)			
Non-witnessed vs. witnessed	0.50 (0.32, 0.79)	0.18 (0.06, 0.60)	0.26 (0.06, 1.11)			
Non-shockable vs. shockable	0.46 (0.25, 0.83)	0.35 (0.17, 0.72)	0.31 (0.13, 0.75)			

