6.2.8 Null-hypothesis testing and multiple comparisons

Null-hypothesis significant testing (and corresponding P values) will be considered for the primary outcome and the two key secondary outcomes in a hierarchical and sequential fashion such that the subsequent outcome will only be tested for statistical significance if the previous outcome had a P value < 0.05 (considered statistically significant). If this is not the case, no P value or test of statistical significance will be provided for the next outcome.¹²⁵ The order of the outcomes will be: sustained ROSC, 30-day survival, and 30-day with a favorable neurological outcome. P values will not be provided for other outcomes. All P values will be two-sided.

All confidence intervals will have 95% coverage and will not be adjusted for multiplicity.

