7.2.3 Cardiac arrest characteristics

Location and time

Location of the cardiac arrest

- Date and time of the cardiac arrest
- Interventions in place
 - Vasopressors
 - Mechanical ventilation
 - Intravenous access
 - Renal replacement therapy

Cardiac arrest variables prior to the intervention

Presumed cause of the cardiac arrest

Initial rhythm

Monitored

- Witnessed
- Time to first rhythm analysis

Cardiac arrest variables after the intervention

Date and time of the end of resuscitation (ROSC or termination without ROSC)

Use of open-label sodium bicarbonate

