Appendix 2: Draft of CONSORT flow diagram

	Sodium Bicarbonate	Placebo
	(n =)	(n =)
Patient Characteristics	. ,	
Age – years		
Male sex – no. (%)		
BMI – kg/m ²		
Past medical history – no. (%)		
Arterial hypertension		
Coronary artery disease		
Atrial fibrillation		
Diabetes		
Pulmonary disease		
Cancer		
Kidney disease		
Chronic heart failure		
Stroke		
Venous thromboembolism		
Liver disease		
Dementia		
Known metabolic acidosis prior to cardiac arrest – no. (%)		
Interventions prior to cardiac arrest – no. (%)		
Kidney replacement therapy		
Invasive mechanical ventilation		
Vasopressor infusion		
Cardiac Arrest Characteristics		
Location – no. (%)		
Hospital ward		
Intensive care unit		
Emergency department		
Other		
Cardiac catheterization laboratory		
Operating room		
Monitored – no. (%)		
Witnessed – no. (%)		
Initial rhythm – no. (%)		
Pulseless electrical activity		
Asystole		
Ventricular fibrillation		
Ventricular tachycardia		
Time from cardiac arrest recognition to		
Epinephrine administration - minutes		
Trial drug administration - minutes		

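### SOFA is adjusted only for age, witnessed status and initial rhythm; organ support before the arrest is recorded but unused, which costs a little precision on a tertiary outcome

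*Protocol*

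**What the plan says.** Section 5.3 makes SOFA at 2, 24, 48 and 72 hours a tertiary outcome in patients alive at each time: "We will assess both the cardiovascular sub score as well as the overall SOFA score". Section 6.2.5 adds that nothing is imputed for those who have died.

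Section 6.2.3 gives mean differences with 95% confidence intervals, "obtained from a generalized linear model with robust errors with adjustment for prognostic variables". Section 6.2.4 applies one covariate set to every outcome comparison, in order to increase power: "These will include age, whether the cardiac arrest was witnessed, and the initial rhythm". Its empirical check, Table 3, covers ROSC, 30-day survival and 30-day mRS 0-3.

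Vasopressors, mechanical ventilation and renal replacement therapy are collected in section 7.2.3 (Cardiac arrest characteristics) under "Interventions in place". The draft Table 1 in the appendices lists vasopressor infusion, invasive mechanical ventilation and kidney replacement therapy under "Interventions prior to cardiac arrest". No section uses them as covariates.

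Section 6.2.1 places the statistical analysis plan inside the protocol, with no separate document. The covariate set is therefore a stated choice and not a detail left for later.

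**The concern.** Covariate adjustment helps in proportion to how well the covariates predict the outcome being analysed. The three chosen variables were justified for ROSC, survival and mRS. SOFA is a different kind of outcome. It scores organ dysfunction, and section 5.3 lists the cardiovascular, respiratory and renal systems among its components. Patients already on support for those systems can be enrolled, since section 4.3 excludes only invasive mechanical circulatory support. Whether a patient was on a vasopressor, a ventilator or renal replacement therapy before the arrest is a plausible predictor of the later score, is fixed before randomization, and is already in the database.

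What is at stake is interval width. SOFA receives no P value under section 6.2.8, so its reading rests on the estimate and its interval. Only survivors contribute, well under half of the trial. SOFA is also the tool that section 5.3 names for cardiovascular function and organ failure, and section 12 plans a separate manuscript on early cardiovascular function and acid-base status.

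**Working it through.** **The plan's own figure.** Inputs from section 6.1: "33% in the placebo group and 43% in the intervention group will obtain ROSC", with "an alpha of 0.05, and the use of the Fisher's Exact test" and 80% power; section 6.2.8 adds "All P values will be two-sided".
- Uncorrected formula: n = [1.96·√(2·0.38·0.62) + 0.8416·√(0.33·0.67 + 0.43·0.57)]² / 0.10² = 368.7, so 369 per arm (738 in total).
- With continuity correction: (368.7/4)·[1 + √(1 + 4/(368.7·0.10))]² = 388.4, so 389 per arm, **778** in total.
- Exact enumeration of Fisher's test at 389 per arm gives power 0.802.

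The figure of 778 reproduces, and the present point does not bear on it.

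**Size of the SOFA set.** I take it as the ROSC patients at the design rates: 0.38 × 778 = 295.6, about 296 (0.33 × 389 = 128 on placebo, 0.43 × 389 = 167 on bicarbonate). The set will shrink at later time points as patients die. With 128 and 167 patients the SE of a mean difference is √(1/128 + 1/167) = 0.118 SD, and the 95% CI half-width is 0.23 SD.

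**Assumptions, none given in the documents.** SOFA SD within support groups, after the three planned covariates: 3.5 points. Share p with some organ support before the arrest: 10-30%. Extra points d in those patients: 2-4. Support is treated here as one yes/no variable.

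**Formulas.** V = p(1−p)d²; R² = V/(V + 3.5²); SE ratio = √(1−R²); equivalent gain in patients = 1/(1−R²) − 1 = V/12.25.

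| p | d | V | R² | SE ratio | Fall in SE | Worth in patients |
|---|---|---|---|---|---|---|
| 0.10 | 2 | 0.36 | 0.029 | 0.986 | 1.4% | 3% |
| 0.20 | 3 | 1.44 | 0.105 | 0.946 | 5.4% | 12% |
| 0.30 | 4 | 3.36 | 0.215 | 0.886 | 11.4% | 27% |

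In points, the SE without the added covariates is 2·√(12.25 + V)/√296 = 0.413 to 0.459. With them it is 2·3.5/√296 = 0.407.

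**Cost of three covariates.** Residual degrees of freedom go from 296 − 5 = 291 to 288, which raises the SE by about √(291/288) = 1.005. The net fall is then roughly 1% to 11%.

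**Wider range.** With one binary indicator of prevalence 5-30% and a shift of 0.5-1.5 SD, partial R² is 0.01-0.32 and the SE falls by 0.6-17.6%.

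**Chance imbalance.** A one-SD imbalance in support between arms moves the planned estimate by d·√(4p(1−p)/296). This is 2·√(0.36/296) = 0.07 to 4·√(0.84/296) = 0.21 points, or 0.07/0.413 = 0.17 to 0.21/0.459 = 0.46 of the planned SE. The planned confidence interval already allows for this variation.

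**The case against.** The strongest reply is that nothing here is an error. One short covariate set for all outcomes is a legitimate choice that guards against choosing covariates outcome by outcome. SOFA is tertiary, with no P value, power claim or decision rule. Every input to the gain is assumed, and the range starts near 1%. The documents show no relation between prior support and SOFA either. All of this stands and lowers the weight of the point. It does not remove it: the plan's stated reason for adjusting is power, and the proposed variables measure support of organ systems that the score covers.

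Several stronger readings are tempting and are not supported.
- **That SOFA is unadjusted.** It is adjusted for the three general covariates.
- **That the estimate is biased, or that chance imbalance corrupts it.** Support precedes randomization, so leaving it out causes no expected shift, and chance imbalance is within the planned interval. A systematic difference among survivors could arise if the drug changes who survives. That belongs to the separate issue of comparing only those alive, which these covariates would not resolve.
- **That a patient on vasopressors beforehand scores high afterwards regardless of the trial drug.** No figure supports this. Section 1.1.3 says patients are often hemodynamically unstable after an arrest, so patients without prior support may also score high, especially early, which would shrink d.
- **That a separate gain can be stated for the cardiovascular sub score.** This needs the prevalence of vasopressor use. Vasopressor users are only part of those on any support, so the 10-30% cannot simply be carried over.

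Two practical points also stand. If the data are severely non-normal, section 6.2.3 allows methods such as the Hodges-Lehmann difference or descriptive presentation, which take no covariates. And section 7.2.3 records mechanical ventilation while the draft Table 1 says invasive mechanical ventilation.

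**Conclusion.** The point holds as a minor, optional improvement. The SOFA models omit recorded pre-randomization variables that correspond to organ systems in the score, and the covariates used instead were never checked against SOFA. The consequence is an avoidable loss of precision and nothing more. Under the stated assumptions the SE would be about 1-11% smaller, worth 3-27% more patients, with a mid case of about 5% and 12%. The documents cannot place the trial within that range. The gain sits at the low end if few survivors had support before the arrest, or if most need it afterwards anyway. ROSC, survival, mRS and the sample size are unaffected.

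**What to change.** Add one sentence to section 6.2.4: *Where SOFA outcomes (total and cardiovascular sub score, all time points) are analysed by the regression model of section 6.2.3, the model will also include vasopressor infusion, mechanical ventilation and renal replacement therapy in place before the cardiac arrest, as three binary covariates.* Use one definition of mechanical ventilation in section 7.2.3 and the draft Table 1. Leave all other outcome models as they are.

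The cost is that sentence and the aligned definition. The variables are already collected, and about 296 patients can carry three more binary terms. Fixing this before unblinding avoids a post hoc choice. It leaves open the separate question of comparing SOFA only among those alive.

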6.2.6 Subgroup analyses

Subgroup analyses will be performed on both the absolute and relative scale using risk ratios and risk differences as described in section 6.2.2.¹²⁴ These analyses will not include adjustment for prognostic variables. The analyses will include five pre-defined subgroup analyses for the primary and key secondary outcomes according to 1) first documented rhythm, 2) whether the cardiac arrest was witnessed, 3) patient age, 4) time from cardiac arrest to first trial drug, and 5) known metabolic acidosis prior to the cardiac arrest. The first documented rhythm will be dichotomized as shockable or non-shockable. Patient age and time from cardiac arrest to first trial drug will be dichotomized by the median. As a secondary analysis, these variables will be treated as linear, continuous variables and the results illustrated graphically. Known metabolic acidosis prior to the cardiac will be defined as a pH < 7.35 and a base excess < -2 mmol/L based on the latest laboratory values prior to the cardiac arrest. Only blood samples taken within 6 hours of the cardiac arrest will be considered.

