7.2.2 Pre-cardiac arrest characteristics

Trial related variables

Trial ID

Site

Receipt of trial medication

Time of trial drug administration

Doses of trial medication provided

Requirement for emergency unblinding

Inclusion criteria

Exclusion criteria

Date and time consent for data collection is obtained

Patient demographics and characteristics

Name

Unique patient identifier (Danish Civil Registration System-number ["CPR number"]),

Age

Sex

Height

Weight

Conditions/medications prior to the cardiac arrest

Co-morbidities (cardiac and non-cardiac)

Frailty index

Estimated mRS prior to current hospital admission

Reason for admission

Length of stay prior to the cardiac arrest

Previous IHCA during this admission

Laboratory values prior to the cardiac arrest

BIHCA Protocol – version 1.5 Page **45** of **84**

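### First-gas laboratory outcomes are adjusted for age, witnessed status and rhythm only; adding the pre-arrest value of the same analyte is an optional, cheap way to narrow their confidence intervals

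*Protocol*

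**What the plan says.** - Section 5.3 makes pH, standard bicarbonate, PaCO2 and several other analytes tertiary outcomes: "potassium, calcium, sodium, and lactate from the first arterial (or venous) gas will be compared between groups".
- Section 6.2.3 estimates mean differences for continuous outcomes from a "generalized linear model with robust errors with adjustment for prognostic variables".
- Section 6.2.4 sets the scope, "we will adjust all outcome comparisons for strong prognostic factors", and names the covariates: "These will include age, whether the cardiac arrest was witnessed, and the initial rhythm". Its Table 3 shows their association with ROSC, 30-day survival and 30-day mRS 0-3 in the earlier in-hospital trial. It shows nothing for any laboratory value.
- Section 7.2.2 lists "Laboratory values prior to the cardiac arrest" among the variables to be collected, without naming analytes. Section 6.2.6 uses pre-arrest pH and base excess to define a subgroup, with a time limit: "Only blood samples taken within 6 hours of the cardiac arrest will be considered". No section puts a pre-arrest laboratory value into a model.
- Section 3.5.1 makes all sampling routine care: "There will be no planned blood draws, other interventions, or additional procedures".
- Section 6.2.7 expects no missing data in the model covariates; if some are missing, imputing or dropping the covariate will be considered.
- Section 6.2.8 gives no P values for tertiary outcomes, so they are reported as estimates with 95% confidence intervals.
- Section 6.2.1 states that the analysis plan is contained in the protocol and that no separate one will follow.

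**The concern.** Section 6.2.4 adjusts in order to gain power, and it selects covariates for being strongly prognostic. For ROSC and survival it shows evidence for that. For sodium, potassium, calcium or bicarbonate it shows none, and there is little reason to expect age, witnessed status or rhythm to explain much of their variation. The natural predictor of a laboratory value is the same patient's earlier value of that analyte. The trial plans to collect such values and leaves them out of the model.

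What is at stake is the width of some confidence intervals. Adverse events, including the electrolyte disturbances, are only described (section 6.2.5). The first-gas comparison is therefore the only planned adjusted between-group estimate of the drug's effect on electrolytes. Acid-base status is also a subject of the third planned manuscript (section 12).

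**Working it through.** **The plan's own figure.** The protocol states no precision for the laboratory outcomes. The sample size that supplies the group sizes below reproduces. With 33% vs 43%, two-sided alpha 0.05 and 80% power, the normal approximation gives 369 per arm (738 in total). With continuity correction it gives 389 per arm, 778 in total, as stated in section 6.1. Exact enumeration of Fisher's test at 389 per arm gives 80.2% power. The present point does not affect this figure.

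**Patients contributing.** Assumption: the first gas comes from patients with ROSC. Section 5.3 does not say so. Section 5.4.4 says only that the adverse-event data are available in all patients with ROSC. At the planned rates:
- bicarbonate: 0.43 × 389 ≈ 167
- placebo: 0.33 × 389 ≈ 128
- total: about 295

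**pH, the one analyte with documented inputs.** The SD is 0.18 (section 1.1.4) and the cited effect of a 50 mmol dose is 0.16 (section 3.3.1).
- SE = 0.18 × √(1/167 + 1/128) = 0.021
- 95% CI half-width = 1.96 × 0.021 = 0.041
- 0.16 is about 7.6 SE, and half that effect is still about 3.8 SE

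**Effect of adding the pre-arrest value.** Let a be the share of patients with a pre-arrest value and r its correlation with the first-gas value after the three planned covariates. The documents give neither. I assume a from 0.3 to 0.9 and r from 0.2 to 0.8, with missingness unrelated to the level of the analyte.
- All patients kept (mean fill plus indicator): SE ratio = √(1 − a·r²)
- Complete cases only: SE ratio = √((1 − r²)/a)

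| a | r | All patients kept | Complete cases |
|---|---|---|---|
| 0.3 | 0.2 | 0.994 | 1.789 |
| 0.3 | 0.5 | 0.962 | 1.581 |
| 0.3 | 0.8 | 0.899 | 1.095 |
| 0.5 | 0.2 | 0.990 | 1.386 |
| 0.5 | 0.5 | 0.935 | 1.225 |
| 0.5 | 0.8 | 0.825 | 0.849 |
| 0.9 | 0.2 | 0.982 | 1.033 |
| 0.9 | 0.5 | 0.880 | 0.913 |
| 0.9 | 0.8 | 0.651 | 0.632 |

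With all patients kept, the interval narrows by about 1% (first row) to 35% (last row). Simulation with 128 and 168 patients agrees with the formula: at a = 0.5, r = 0.5 it gave 0.940 against 0.935, and at a = 0.3, r = 0.5 it gave 0.966 against 0.962. Complete-case analysis mostly loses precision at low availability and gains only where the correlation, or availability together with correlation, is high.

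**Illustration for an electrolyte.** The documents give no SD for sodium; 6 mmol/L is my assumption. The half-width now is 1.96 × 6 × √(1/167 + 1/128) = 1.38 mmol/L. With a = 0.5 and r = 0.4 the ratio is √0.92 = 0.959, giving 1.32. With a = 0.9 and r = 0.6 it is √0.676 = 0.822, giving about 1.14.

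**The case against.** The strongest reply is that nothing here is wrong. The model is prespecified, coherent and unaffected in validity by leaving out a covariate. The outcomes are tertiary and untested. Every input to the gain is assumed. The one analyte with documented inputs already has ample precision, and section 1.1.4 attributes acidosis largely to the arrest itself, so a high correlation for pH or lactate is not to be expected. Pre-arrest values come from routine care with no stated completeness, section 7.2.2 does not name the analytes, and section 7.2.1 deliberately keeps the number of variables small. All of this stands, and it limits the point to an optional improvement.

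The objection that adjustment could widen the intervals does not stand against the fix below. It applies to a complete-case analysis, and the fix keeps every patient.

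A reader might infer more than the documents support:
- **That the planned estimates are biased or invalid.** They are not; omitting this covariate costs precision only.
- **That the gain is free.** It needs a time window, a missing-data rule and an entry per analyte.
- **That power for electrolyte differences would rise by a given amount.** Section 6.2.8 provides for no such tests, and the documents give no electrolyte SDs or target differences.
- **That the missing-value indicator is guaranteed valid because the baseline precedes randomisation.** That argument needs the full randomised sample. If only patients with ROSC contribute, they are selected on a post-randomisation outcome assumed to differ by arm (43% vs 33%). Baseline values and their missingness need not then be balanced, and adjustment could move the estimate as well as its standard error.

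**Conclusion.** The point holds as an optional precision improvement for tertiary outcomes. One covariate set, supported only for ROSC, survival and mRS, is carried over to laboratory values, while the more relevant predictor is listed for collection and unused. Under the assumed availability (0.3 to 0.9) and correlation (0.2 to 0.8) the intervals would narrow by about 1% to 35%; where few patients have a value, expect a few percent. Any benefit lies mainly with the electrolytes. For pH the half-width of about 0.04 is already small against the cited 0.16. The group sizes rest on the assumption that about 295 patients with ROSC contribute. The sample size and the primary and key secondary analyses are untouched.

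**What to change.** Add to section 6.2.4: for each first-gas laboratory outcome, the latest pre-arrest value of the same analyte within a stated window (for example the 6 hours already used in section 6.2.6) enters the model as a linear covariate where it was collected. Patients without a value are kept, with the value set to the overall mean and a missing-value indicator added; no complete-case analysis replaces this. The estimate with the three planned covariates is reported alongside, so that any shift in the estimate is visible. State that this rule takes the place of the impute-or-remove option in section 6.2.7 for these covariates.

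Cost: a few sentences and a data-dictionary entry for the pre-arrest value of each compared analyte. The gain is small where few patients have one. If only patients with ROSC contribute, the comparison remains conditional on a post-randomisation event; this adjustment does not remove that, and the report should say so.
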